## 9 TREATMENT OF SUBJECTS

### 9.1 Treatments

#### 9.1.1 Description of Study Drug and Dosing Regimen

Arginine hydrochloride is a semi-essential amino acid, which is available in purified powder form in bulk from many sources throughout the United States. After shipment to the contract pharmacy, the arginine hydrochloride will not be modified further. It will, however, be encapsulated into 250 and 500mg gelatin capsules by the contract pharmacy (Abbott's Compounding, Oakland, CA). Appropriate control capsules will also be produced by the contract pharmacy.

Two doses of arginine hydrochloride will be evaluated in this trial; however, one dose (0.10 g/kg/day) has been discontinued. Patients in each age group (children and adult) will be treated with one dose of arginine (0.05 g/kg/day ) or placebo divided for BID dosing. Sixteen patients will be randomized to each dose level and placebo. Patient dose will be calculated according to the patient's weight. Thus, pediatric subjects may be given 500 mg capsules if they have a high enough weight and adult subjects may be given 250 mg capsules if they have a low enough weight. The same dose will be given each day. The maximum dose will be 10g of arginine per day. Patients unable to ingest the capsules (e.g. children) will be able to open capsules and mix with food or liquid. The research pharmacist at each institution will distribute a one month's supply of arginine at each clinic visit. Patients and study personnel will be blinded as to whether the patient is receiving arginine or placebo. Capsule counts will be performed once a month at Visits 6, 7, and 8 to assess overall compliance with the therapy. Unused medication will be returned to the pharmacy after the capsules have been counted.

### 9.1.2 Dose Modification or Interruption of Study Drug

While oral arginine has been shown to have little toxicity when given in the doses outlined in this study, we will closely monitor signs, symptoms, and laboratory findings to assess for unexpected toxicities. Arginine will be discontinued in any patient who experiences the following:

- Drop in hemoglobin below 5gm/dL
- Pulmonary failure requiring intubation
- Hepatic dysfunction (SGPT  $\geq$  3X normal and albumin  $\leq$  3.0)
- Renal dysfunction (Creatinine  $\geq$  1.4 for children and  $\geq$  1.6 for adults)
- Focal neurological changes
- Increase in methemoglobin level to  $>2X$  normal level
- Apparent allergic reaction to arginine
- Severe headache
- Pregnancy

### 9.1.3 Packaging, Labeling, and Blinding of Study Drug

The U. S. Department of Health and Human Services Supply Services Center will be used to package, label and blind study drug.

### 9.1.4 Return and Destruction of Study Drug(s)

All unused study drug will be returned to the local pharmacy and destroyed appropriately.

## 9.2 Randomization and Masking

Randomization will be stratified by center and age group to preserve a balance across treatment groups. No other stratification factors will be used and a block randomization method will be used to ensure balance within the center-age strata. A randomization list for each center and age group will be generated by the SDMC and kept at the SDMC. The pharmacist dispensing study drug at the site will have access to this list. Additionally, emergency unblinding envelopes will be generated and sent to the sites. These will be labeled with the subject's ID on the outside and can be opened to reveal the randomized dose in case of an emergency. After the completion of the trial, all sealed randomization envelopes will be returned to the SDMC for confirmation of maintenance of the mask.

## 9.3 Prior and Concomitant Therapy

Patients enrolled in this trial will receive all therapy and monitoring that is considered standard of care for patients with SCD.

Table 9.1 Medications Requiring a Washout Prior to Study Drug Dosing

Medication Requiring a Washout Period Prior to Study Drug Dosing	Washout Period
Hydroxyurea	90 days
Transfusion	90 days
Arginine	90 days

#### 9.4 Subject Compliance

Plasma arginine concentration will be measured throughout the study, as a measure of subject compliance.

#### 9.5 Study Procedures

##### 9.5.1 Visit One

At Visit 1 (Week -4, Study Day -28), the first screening visit will occur. The patient must have a signed consent form on file and the inclusion and exclusion criteria will be checked to make sure that the patient is eligible for the study. Blood will be drawn so that the chemistry and hematology labs can be done locally. These tests include the Chemistry panel, LDH, CBC, Reticulocytes, Met Hb, Urinalysis, and Urine BHCG. Both males and females will complete a urinalysis and females will also be screened for pregnancy if they are of childbearing potential. The amount of blood drawn for the local labs will vary between sites. Blood will also be drawn and sent to two different central labs. Approximately a total of 30 ccs (or 6 tsp) will be drawn from the patient. One sample of blood will be sent to the Boston labs where Advia and Gardos Channel tests are performed. The other samples of blood will be sent to Oakland where the Free Radicals, Nitric Oxide, sVCAM-1, Arginine, Arginase and the Ektacytometry tests are performed. In addition to the blood work, personal information will be collected from the patient, including hospitalization, ER and clinical, demographic, medication history, pain history, and concomitant medication.

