## 8 SELECTION AND WITHDRAWAL OF SUBJECTS

### 8.1 Inclusion Criteria

Subjects who meet all of the following criteria are eligible for enrollment into the study:

1. Participant has signed the informed consent.
2. Established diagnosis of Hb SS or S-beta thalassemia
3. History of at least one vaso-occlusive pain events in last 12 months
4. Regular compliance with comprehensive care
5. Aged 5 years or greater
6. Patient is in his/her steady state and not in the midst of any acute complication due to sickle cell disease at enrollment

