### 8.3 Subject Discontinuation

Subjects may decide to discontinue participation at any time during the study. Investigators may discontinue any subject at their discretion, if in their professional opinion, the subject's health, safety, and/or well-being is threatened by continued participation in the study. The following circumstances require discontinuation of subjects:

1. Drop in hemoglobin below 5gm/dL
2. Pulmonary failure requiring intubation
3. Hepatic dysfunction (SGPT  $\geq$  3X normal and albumin  $\leq$  3.0)

4. Renal dysfunction (Creatinine  $\geq 1.4$  for children and  $\geq 1.6$  for adults)
5. Focal neurological changes
6. Increase in methemoglobin level to  $> 2X$  normal level
7. Apparent allergic reaction to arginine
8. Severe headache
9. Pregnancy

Adverse events caused by participation in the study may necessitate modifications to the level of participation of a subject or discontinuation of subjects from participation in the study. Subjects who discontinue early from the study will be replaced.

Subjects who discontinue prematurely from the study for any reason will be encouraged to complete the lab evaluations required at Visit 10; these include a urinalysis, the chemistry and hematology panels, central lab evaluations, and completion of the interim health history form. These follow-up evaluations will be conducted as soon as the patient is able to come back in for one follow-up visit.

In the event that a local principal investigator wishes to discontinue a subject at his or her discretion (i.e. not due to one of the criteria listed above) then the investigator must contact the study Principal Investigator, [name], to formalize discontinuation.

[figure not shown]

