##### 9.5.2 Visit Two

At Visit 2 (Week -2, Study Day -14), blood will be collected for the two central labs as in Visit 1. Female patients of childbearing potential will receive a pregnancy test. Medical information will be collected including hospitalization and pain information, concomitant medication information, and AE information. The discontinuation criteria will be checked to make sure that the patient is still eligible for the study.

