##### 9.5.3 Visit Three Randomization

At Visit 3 (Week 0, Study Day 0), the Baseline/Study Entry Visit, blood will be drawn for both the central and local labs in the same manner that it was collected during Visit 1. A urinalysis will be performed and female patients of childbearing potential will receive

a pregnancy test. All patients will receive an echocardiogram. Hospitalization, pain, concomitant medication, and AE information will be collected. For all patients presenting with chest pain or cardiac events, an EKG will be done and CPK isoenzymes and troponin levels will be measured. The study coordinator will double-check the discontinuation criteria prior to randomizing the patient and distributing enough of the study drug for one month.

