#### 9.5.4 *Visit Four*

At Visit 4 (Week 1, Study Day  $7 \pm 1$ ), the patient will have been receiving the study drug for one week. The blood will be drawn for both the local and central labs in the same manner that it was collected for Visit 1 and Visit 3. A urinalysis will be performed and female patients of childbearing potential will receive a pregnancy test. A urine sample will be collected for the urinalysis and a pregnancy test (for female patients of childbearing potential). Hospitalization, pain, concomitant medication, and AE information will be collected. For all patients presenting with chest pain or cardiac events, an EKG will be done and CPK isoenzymes and troponin levels will be measured. The discontinuation criteria will be checked to make sure the patient is still eligible for the study.

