#### 9.5.5 *Visit Five*

At Visit 5 (Week 2, Study Day  $14 \pm 1$ ), the patient will have been receiving the study drug for two weeks. The blood collected for the central labs will be done in the same manner as in Visits 1, 2, 3, and 4 (except for ET-1 and sVCAM-1). Enough blood will be collected for the local labs to perform the Chemistry panel, LDH, CNC, and Reticulocytes tests. Female patients of childbearing potential will receive a pregnancy test. Hospitalization, pain, concomitant medication, and AE information will be collected. For all patients presenting with chest pain or cardiac events, an EKG will be done and CPK isoenzymes and troponin levels will be measured. The discontinuation criteria will be checked to confirm the patient is still eligible for the study.

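### The research draw of about 30 cc ignores weight and age at eight visits; the lightest children would give roughly 7–14% of an assumed blood volume between Week −4 and Week 4

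*Protocol*

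**What the plan says.** Protocol section 9.5.1 (Visit One) describes local and central laboratory blood together. On the local part it says "The amount of blood drawn for the local labs will vary between sites". After introducing the two central laboratories it says "Approximately a total of 30 ccs (or 6 tsp) will be drawn from the patient". No other volume appears in the visit procedures.

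Later visits refer back to this one:
- Visit 2 (9.5.2): "blood will be collected for the two central labs as in Visit 1".
- Visit 3 (9.5.3): "in the same manner that it was collected during Visit 1".
- Visit 4 (9.5.4): "in the same manner that it was collected for Visit 1 and Visit 3".
- Visits 6, 7, 8 and 10 (9.5.6, 9.5.7, 9.5.8, 9.5.10) use similar wording.
- Visit 5 (9.5.5) has the central panel "except for ET-1 and sVCAM-1", and Visit 9 (9.5.9) leaves out the free-radical and endothelial tests. Neither visit has a stated volume.

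The age criterion in section 8.1 is "Aged 5 years or greater". Sections 8.1 and 8.2 set no minimum weight or haemoglobin. Section 8.3 makes discontinuation mandatory for "Drop in hemoglobin below 5gm/dL".

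**The concern.** The volume is the same for a five-year-old and an adult, although the protocol adjusts for size or age elsewhere: dose by weight in 9.1.1, and creatinine limits by age group in 8.2 and 8.3. The patients have a haemolytic anaemia (5.1), and 48 of the 94 planned patients are children (7.2).

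Two things are at stake. The first is blood loss in the lightest children that serves no purpose beyond the assays and could be reduced. The second is measurement. Repeated bleeding can lower haemoglobin and bring younger cells into the circulation. Haemoglobin and reticulocytes are monitored for safety (11.1), and red-cell density, the percentage of cells above 41, is a primary endpoint (12.4.2). The densest sampling runs from four weeks before randomisation to Week 4, so it could disturb both baseline and early post-baseline readings.

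**Working it through.** **Inputs from the protocol.** 30 mL per full draw (9.5.1). Visits at Weeks −4, −2, 0, 1, 2, 4, 8, 12, 14 and 16 (7.2.2). Reduced panels at Weeks 2 and 14 (9.5.5, 9.5.9).

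**Inputs assumed, because the protocol gives none.** Body weight 15–25 kg for the smallest children; blood volume 70–80 mL/kg. Total blood volume is then 15 × 70 = 1,050 mL to 25 × 80 = 2,000 mL.

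**The protocol's own figure.** 6 teaspoons × 5 mL = 30 mL, so the two units in 9.5.1 agree.

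**Draws in the densest eight weeks (Week −4 to Week 4).** There are six visits: five full (Weeks −4, −2, 0, 1, 4) and one reduced (Week 2).
- Full draws only: 5 × 30 = 150 mL.
- Week 2 counted at half, for illustration: 150 + 15 = 165 mL.
- Week 2 counted as full (ceiling): 6 × 30 = 180 mL.
- Reading most favourable to the plan: 30 cc is the whole-visit total including local blood. Visit 2, which takes central blood only, would then need less than 30 cc. Leaving out Visits 2 and 5 entirely and counting Visits 1, 3, 4 and 6: 4 × 30 = 120 mL.

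**Share of blood volume** = volume drawn ÷ (kg × mL/kg):

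| Volume | 25 kg, 80 mL/kg | 15 kg, 70 mL/kg |
|---|---|---|
| 120 mL | 120/2,000 = 6.0% | 120/1,050 = 11.4% |
| 150 mL | 150/2,000 = 7.5% | 150/1,050 = 14.3% |
| 165 mL | 165/2,000 = 8.3% | 165/1,050 = 15.7% |
| 180 mL | 180/2,000 = 9.0% | 180/1,050 = 17.1% |

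For comparison, an adult of 70 kg at 70–80 mL/kg (4,900–5,600 mL) would give 150/5,600 = 2.7% to 180/4,900 = 3.7%.

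**Other windows.** Weeks 0–8: four full and one reduced draw, 120–150 mL. Weeks 8–16: three full and one reduced, 90–120 mL. Whole study: eight full draws = 240 mL, at most 300 mL.

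If local blood is additional, which is the more natural reading of 9.5.1, every figure except the 120 mL row is too low by an amount the protocol does not give.

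**The case against.** The strongest points on the other side are these.

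- **The volume is stated once.** A reader might infer a flat 30 cc at all ten visits. The protocol does not support that: Visits 5 and 9 are reduced, and the cross-references repeat the manner of collection, not the number. This stands, so the full volume is applied here to eight visits only, and 17.1% is a ceiling.
- **The 30 cc is ambiguous.** It may cover local as well as central blood. This also stands. The lowest reading still gives 6.0–11.4%, and an ambiguity in an operative volume is a reason to rewrite it.
- **The percentages depend on outside assumptions and add up draws over eight weeks without allowing for red-cell replacement.** Correct. They describe the cumulative volume removed, not a net deficit. A single draw is 30/2,000 = 1.5% to 30/1,050 = 2.9%.
- **Monitoring exists.** A blood count is scheduled at nine of ten visits (7.2.2, 11.1.2), a haemoglobin discontinuation rule and investigator discretion are in 8.3, and a safety board is described in 13.1. These may detect a problem; none limits the volume drawn.
- **A limit may sit elsewhere.** Consent pages are not available, 11.3.3 mentions a manual of procedures, and the ektacytometry text in 10.1.2 mentions collection instructions sent to sites. So absence can be claimed only for the text shown. A limit elsewhere would still leave 9.5.1 giving an unscaled instruction without reference to it.
- **Few children are affected.** Of the 48, 16 were already randomised to the earlier high-dose arm (7.2), so at most 48 − 16 = 32 belong to the arms still recruiting, and only the lightest of those are at issue. This narrows the reach, not the defect.

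**Conclusion.** The point holds as a safety and data-quality improvement for the lightest children. Followed as written, the protocol takes about 150 mL, at most 180 mL, of research blood between Week −4 and Week 4 regardless of body size. Under the assumed 15–25 kg and 70–80 mL/kg this is 7.5–14.3% of blood volume, with a ceiling of 17.1%, or 6.0–11.4% on the most favourable reading of the 30 cc.

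Two stronger conclusions are not supported. A reader might infer that the draws bias the treatment comparison. The placebo and arginine arms follow the same schedule, and three of the six draws in the window fall at or before randomisation, so the plausible effect is extra variability. A reader might also infer withdrawals caused by the sampling, through the 5 gm/dL rule. The protocol gives no entry haemoglobin distribution and no basis for estimating a fall, so no number of withdrawals can be derived. The size of any added noise in haemoglobin, reticulocytes or red-cell density is likewise unknown.

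**What to change.** In section 9.5.1:
1. State whether the 30 cc includes local-laboratory blood, and give the volumes at Visits 5 and 9.
2. Replace the flat figure with a weight-scaled volume that counts local plus central blood, under a cumulative per-kg limit agreed with the ethics boards. If a limit already exists in a manual, refer to it here.
3. Fix a tube order for children who cannot give the full volume: NOx, Gardos channel and Advia first, then the secondary assays. Most room for omission is at Week −2, where all secondary laboratory assays are scheduled, and at Week 2, where nitrotyrosine, 8-iso-PGF2α and ektacytometry remain. Week 14 offers little, because of the secondary assays in the 7.2.3 table only ektacytometry is still scheduled there.

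The cost is one protocol table and matching laboratory-manual text, plus some missing secondary-assay values in the lightest children. The protocol gives no tube volumes by assay, so the blood saved by each omission must come from the laboratories.

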##### 9.5.2 Visit Two

At Visit 2 (Week -2, Study Day -14), blood will be collected for the two central labs as in Visit 1. Female patients of childbearing potential will receive a pregnancy test. Medical information will be collected including hospitalization and pain information, concomitant medication information, and AE information. The discontinuation criteria will be checked to make sure that the patient is still eligible for the study.

##### 9.5.3 Visit Three Randomization

At Visit 3 (Week 0, Study Day 0), the Baseline/Study Entry Visit, blood will be drawn for both the central and local labs in the same manner that it was collected during Visit 1. A urinalysis will be performed and female patients of childbearing potential will receive

a pregnancy test. All patients will receive an echocardiogram. Hospitalization, pain, concomitant medication, and AE information will be collected. For all patients presenting with chest pain or cardiac events, an EKG will be done and CPK isoenzymes and troponin levels will be measured. The study coordinator will double-check the discontinuation criteria prior to randomizing the patient and distributing enough of the study drug for one month.

#### 9.5.4 *Visit Four*

At Visit 4 (Week 1, Study Day  $7 \pm 1$ ), the patient will have been receiving the study drug for one week. The blood will be drawn for both the local and central labs in the same manner that it was collected for Visit 1 and Visit 3. A urinalysis will be performed and female patients of childbearing potential will receive a pregnancy test. A urine sample will be collected for the urinalysis and a pregnancy test (for female patients of childbearing potential). Hospitalization, pain, concomitant medication, and AE information will be collected. For all patients presenting with chest pain or cardiac events, an EKG will be done and CPK isoenzymes and troponin levels will be measured. The discontinuation criteria will be checked to make sure the patient is still eligible for the study.

#### 9.5.5 *Visit Five*

At Visit 5 (Week 2, Study Day  $14 \pm 1$ ), the patient will have been receiving the study drug for two weeks. The blood collected for the central labs will be done in the same manner as in Visits 1, 2, 3, and 4 (except for ET-1 and sVCAM-1). Enough blood will be collected for the local labs to perform the Chemistry panel, LDH, CNC, and Reticulocytes tests. Female patients of childbearing potential will receive a pregnancy test. Hospitalization, pain, concomitant medication, and AE information will be collected. For all patients presenting with chest pain or cardiac events, an EKG will be done and CPK isoenzymes and troponin levels will be measured. The discontinuation criteria will be checked to confirm the patient is still eligible for the study.

#### 9.5.6 *Visit Six*

At Visit 6 (Week 4, Study Day  $28 \pm 3$ ), the patient will have been receiving the study drug for four weeks. The blood will be drawn and distributed for both the local and central labs in the same manner that it was collected for Visits 1, 3, and 4. Hospitalization, pain, concomitant medication, and AE information will be collected. For all patients presenting with chest pain or cardiac events, an EKG will be done and CPK isoenzymes and troponin levels will be measured. The discontinuation criteria will be checked to confirm the patient is still eligible for the study. All unused study drug that was distributed at Visit 3 will be collected, counted, and documented. Enough new study drug for one month will be distributed to the patient.

### 9.5.7 Visit Seven

At Visit 7 (Week 8, Study Day  $56 \pm 3$ ), the patient will have been receiving the study drug for eight weeks. The blood will be drawn for the central labs in the same manner that it was collected for Visits 1, 2, 3, 4, and 6. The blood drawn for the local labs will be enough for the Chemistry panel, LDH, CBC, Reticulocytes, and Met Hb tests. Female patients of childbearing potential will receive a pregnancy test. Hospitalization, pain, concomitant medication, and AE information will be collected. For all patients presenting with chest pain or cardiac events, an EKG will be done and CPK isoenzymes and troponin levels will be measured. The discontinuation criteria will be checked to confirm the patient is still eligible for the study. All unused study medication that was distributed at Visit 6 will be collected, counted, and documented. Enough new study drug for one month will be distributed to the patient.

### 9.5.8 Visit Eight

At Visit 8 (Week 12, Study Day  $84 \pm 3$ ), the patient will have been receiving study drug for twelve weeks. The blood will be drawn and distributed for both the local and central labs in the same manner that it was collected for Visits 1, 3, 4, 6, and 7. An echocardiogram will be performed only if the echocardiogram from Visit 3 was abnormal. If the first echocardiogram was normal, a second one will not be performed. The purpose of the echocardiogram is to see if arginine has any effect on pulmonary hypertension in sickle cell patients. A urinalysis will be performed on all patients, and female patients of childbearing potential will receive a pregnancy test. Hospitalization, pain, concomitant medication, and AE information will be collected. For all patients presenting with chest pain or cardiac events, an EKG will be done and CPK isoenzymes and troponin levels will be measured. The discontinuation criteria will be checked to confirm the patient is still eligible for the study. All unused study drug that was distributed at Visit 7 will be collected, counted, and documented.

